### **5.5.2. Safety**

A subject will be considered missing for any given solicited local or general event within Days 0-3 only if the subject does not record any values, either 'yes' or 'no', for the indicated solicited event. If the subject has at least one nonmissing response on at least one day, then the subject will be considered nonmissing for that solicited event.

Subjects with at least 1 unsolicited AE, or with completion date on Day 0 or later, will be eligible for AE analysis.

No missing safety data will be imputed.

## **6. ANALYSES AND SUMMARIES**

This section specifies which endpoints will be analyzed for which cohorts.

**6.1. Immunogenicity Endpoints**

**6.1.1. Primary Endpoints**

The primary endpoint is the booster vaccination response. The primary analysis for this endpoint will use the booster ATP cohort for immunogenicity. For any group, if more than 5% of subjects who have serological results are excluded from the Booster ATP cohort, a second analysis based on the booster TVC will be performed as a sensitivity analysis. Proportions and their 2-sided 95% CIs will be compiled for each meningococcal group.

**Table 4. Primary Endpoint Analyses**

Endpoint	Cohort	Statistical Method/Test
Booster response	Booster ATP cohort for immunogenicity	2-sided exact 95% CI on each proportion
Booster response	Booster TVC	2-sided exact 95% CI on each proportion

Abbreviations: ATP = according to protocol; TVC = total vaccinated cohort.

**6.1.2. Secondary Endpoints**

The secondary endpoints are proportions of subjects achieving indicated meningococcal or tetanus antibody level cutoffs. Both prebooster and postbooster results will be analyzed. Geometric means and their 2-sided 95% CIs will also be compiled for all groups at both prebooster and postbooster visits.

**Table 5. Secondary Endpoint Analyses in Booster ATP Cohort for Immunogenicity**

Endpoint	Cohort	Statistical Method/Test
Proportion of subjects with rSBA titers $\geq 1:8$ for each meningococcal group, both before and after booster vaccination	Booster ATP cohort for immunogenicity	2-sided exact 95% CI on each proportion
Proportion of subjects with rSBA titers $\geq 1:128$ for each meningococcal group, both before and after booster vaccination	Booster ATP cohort for immunogenicity	2-sided exact 95% CI on each proportion
Proportion of subjects with anti-TT concentrations $\geq 0.1$ IU/mL, both before and after booster vaccination	Booster ATP cohort for immunogenicity	2-sided exact 95% CI on each proportion
Proportion of subjects with anti-TT concentrations $\geq 1.0$ IU/mL, both before and after booster vaccination	Booster ATP cohort for immunogenicity	2-sided exact 95% CI on each proportion
GMT and 95% CI for each meningococcal group, both before and after booster vaccination	Booster ATP cohort for immunogenicity	2-sided exact 95% CI on each geometric mean
GMC and 95% CI for TT antibody concentration, both before and after booster vaccination	Booster ATP cohort for immunogenicity	2-sided exact 95% CI on each geometric mean
Tabulation of percentage of subjects with rSBA titers $<1:8$ , $\geq 1:8$ , $\geq 1:16$ , $\geq 1:32$ , etc. for each meningococcal group	Booster ATP cohort for immunogenicity	Incidence proportions

Abbreviations: ATP = according to protocol; GMT = geometric mean titer; rSBA = serum bactericidal assay using rabbit complement; TT = tetanus toxoid.

090177e19088d171\Approved\Approved On: 11-Mar-2019 09:48 (GMT)

If more than 5% of the subjects from either vaccine group who have serological results are excluded from the booster ATP cohort for immunogenicity, then the secondary endpoints (Table 5) will be re-analyzed using the booster TVC.

CCI [Redacted]

CCI [Redacted]

090177e19088d171\Approved\Approved On: 11-Mar-2019 09:48 (GMT)

**6.1.4. Figures**

Reverse cumulative distribution curves (RCDCs) will be constructed for pre- and postbooster immunogenicity values. Separate figures will be compiled for rSBA-MenA, rSBA-MenC, rSBA-MenW-135, rSBA-MenY, and anti-TT. Each figure will include pre- and postbooster curves for ACWY-TT and MenPS groups. The cohort will be the booster ATP cohort for immunogenicity.

**6.1.5. Persistence Analyses**

The persistence analyses will consist of 3 parts.

1. Descriptive statistics (percentage of subjects with titers  $\geq 1:8$ , percentage of subjects with titers  $\geq 1:128$ , GMT) for each time point from Month 0, Month 1, and Month 120. The cohort will be the ATP cohort for persistence at Month 120.

CCI [Redacted]

CCI [Redacted]

CCI [Redacted]

CCI [Redacted]

Tetanus toxoid antibody concentrations will not be included in the persistence analyses.

For any group, if more than 5% of subjects who have serological results are excluded from the ATP cohort for persistence at Month 120, a second analysis based on the total cohort at Month 120 will be performed to complement the ATP analysis.

090177e19088d171\Approved\Approved On: 11-Mar-2019 09:48 (GMT)

**Table 7. Persistence Analyses**

Endpoint	Cohort	Statistical Method/Test
Proportion of subjects with rSBA titers $\geq 1:8$ for each meningococcal group at Month 120	ATP cohort for persistence at Month 120	2-sided exact 95% CI for proportion within each group;  2-sided standardized asymptotic 95% CI for the difference of proportions between ACWY-TT and MenPS groups
Proportion of subjects with rSBA titers $\geq 1:128$ for each meningococcal group at Month 120	ATP cohort for persistence at Month 120	2-sided exact 95% CI for proportion within each group;  2-sided standardized asymptotic 95% CI for the difference of proportions between ACWY-TT and MenPS groups
Ratio of GMTs between ACWY-TT and MenPS for each meningococcal group at Month 120	ATP cohort for persistence at Month 120	ANOVA*
Tabulation of percentage of subjects with rSBA titers $<1:8$ , $\geq 1:8$ , $\geq 1:16$ , $\geq 1:32$ , etc. for each meningococcal group at Month 120	ATP cohort for persistence at Month 120	Incidence proportions

CCI

Abbreviations: ANOVA = analysis of variance; ATP = according to protocol; GMT = geometric mean titer; rSBA = serum bactericidal assay using rabbit complement.

\* Vaccine group as fixed effect in ANOVA model.

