1.2. Rationale for the study and study design

Subjects aged 11-17 years of age were vaccinated with one dose of either MenACWY-TT or *Mencevax ACWY* in study MenACWY-TT-036 (109069). The participants from India and the Philippines were further followed for the assessment of persistence in study MenACWY-TT-043 (112148). Unless they withdrew their consent, subjects were invited for a yearly blood sample, regardless of their serostatus at the previous persistence time point, up to Year 5 after primary vaccination. Five years after vaccination, the percentage of subjects with rSBA titres $\geq 1:8$ for the 4 meningococcal serogroups A, C, W-135, and Y ranged between 86.0% - 97.5% in the *Nimenrix* vaccinees and between 34.9% - 93.0% in the subjects vaccinated with *Mencevax ACWY*.

A booster dose 5 years after vaccination has already been assessed in individuals primed at the age of 11-25 years. The purpose of this study is to evaluate the safety and immunogenicity of a booster dose of MenACWY-TT vaccine administered 10 years after healthy subjects aged 11-17 years received either a single dose of meningococcal serogroup ACWY tetanus toxoid conjugate (MenACWY-TT) vaccine or *Mencevax ACWY*. The primary vaccination study MenACWY-TT-036 (109069) was conducted in India, the Philippines and Taiwan. The MenACWY-TT-043 (112148) persistence study up to Year 5 after primary vaccination included only India and the Philippines. Due to Good Clinical Practice (GCP) issues in India, this booster study will only be conducted in the Philippines.

In order to support assay development, subjects who have voluntarily signed the informed consent document (ICD) addendum will have up to 50 mL, rather than 10 mL, of blood drawn at Visit 2.

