2.2. Secondary objectives

Secondary immunogenicity objectives:

One month post-booster vaccination with MenACWY-TT vaccine:

- To evaluate the immunogenicity of a booster dose of MenACWY-TT conjugate vaccine with respect to the percentage of subjects with rSBA-MenA, rSBA-MenC, rSBA-MenW-135, and rSBA-MenY antibody titers \geq 1:8, \geq 1:128 and Geometric Mean Titres (GMTs).

Pre-booster and one month post-booster vaccination with MenACWY-TT vaccine:

- To evaluate the percentage of subjects with anti-TT concentrations \geq 0.1 IU/mL, \geq 1.0 IU/mL and Geometric Mean Concentrations (GMCs).

Long-term persistence phase ten years after primary vaccination with MenACWY-TT or *Mencevax ACWY* in Study MenACWY-TT-036 (109069):

- To evaluate the long-term antibody persistence induced by MenACWY-TT conjugate vaccine as compared to *Mencevax ACWY* when administered to individuals 11-17 years of age with respect to the percentage of subjects with rSBA-MenA, rSBA-MenC, rSBA-MenW-135, and rSBA-MenY antibody titers \geq 1:8, \geq 1:128 and GMTs.

Secondary safety objectives:

- To evaluate the safety and reactogenicity of a booster dose of MenACWY-TT conjugate vaccine.
- To describe Serious Adverse Events (SAEs) related to study vaccination and any event related to lack of vaccine efficacy (i.e. meningococcal disease) from the

[figure not shown]
subject's last visit in study MenACWY-TT-036 (109069) or in study MenACWY-TT-043 EXT:036 Y2, 3, 4, 5 (112148).*

- *last visit in study MenACWY-TT-036 (109069) will only be considered for subjects who did not participate in study MenACWY-TT-043 EXT:036 Y2, 3, 4, 5 (112148).

Refer to Section 10.2 for the definition of the secondary endpoints.

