### 2.2.2. Secondary Objectives

#### Secondary immunogenicity objectives:

One month post-booster vaccination with MenACWY-TT vaccine:

- Evaluate the immunogenicity of a booster dose of MenACWY-TT conjugate vaccine with respect to the percentage of subjects with rSBA-MenA, rSBA-MenC, rSBA-MenW-135, and rSBA-MenY antibody titers  $\geq$ 1:8,  $\geq$ 1:128 and geometric mean titers (GMTs).

Before the booster vaccination and 1 month after the booster vaccination with MenACWY-TT vaccine:

- Evaluate the percentage of subjects with anti-tetanus toxoid (TT) concentrations  $\geq$ 0.1 IU/mL,  $\geq$ 1.0 IU/mL and geometric mean concentrations (GMCs).

Long-term persistence phase 10 years after primary vaccination with MenACWY-TT or Mencevax ACWY in Study MenACWY-TT-036:

- Evaluate the long-term antibody persistence induced by MenACWY-TT conjugate vaccine as compared to Mencevax ACWY when administered to individuals 11-17 years

of age with respect to the percentage of subjects with rSBA-MenA, rSBA-MenC, rSBA-MenW-135, and rSBA-MenY antibody titers  $\geq 1:8$ ,  $\geq 1:128$  and GMTs.

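### The Month 120 GMT ratio is compared by vaccine group alone, although each subject's Month 0 titre is held; an adjusted ratio should be reported beside it

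*SAP*

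**What the plan says.** The secondary persistence objective (SAP 2.2.2, and likewise Protocol 2.2) is to "Evaluate the long-term antibody persistence induced by MenACWY-TT conjugate vaccine as compared to Mencevax ACWY", measured by the percentages with rSBA titres of at least 1:8 and at least 1:128 and by GMTs.

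SAP Table 7 makes the between-group comparison at Month 120 in two ways. For the two percentages it gives a "2-sided standardized asymptotic 95% CI for the difference of proportions between ACWY-TT and MenPS groups", with no stratification stated. For titres it lists "Ratio of GMTs between ACWY-TT and MenPS for each meningococcal group at Month 120", analysed by ANOVA, with the footnote "Vaccine group as fixed effect in ANOVA model". No covariate is named.

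Month 0 is not ignored. Part 1 of SAP 6.1.5 gives the two percentages and the GMT "for each time point from Month 0, Month 1, and Month 120. The cohort will be the ATP cohort for persistence at Month 120". These are group summaries, and they do not link a subject's Month 120 titre to that subject's Month 0 titre. Month 0 titre is not among the baseline variables in SAP 3.3, and the persistence cohort in SAP 4.5 neither excludes nor separates subjects already at or above 1:8 before primary vaccination.

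SAP 6.1.5 announces three parts, of which only the first is readable. Part of Table 7 and the methods after SAP 5.2.1 are also blacked out. SAP 4.7 defines an adapted cohort that includes Month 0, for a modelling analysis that cannot be read.

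**The concern.** A subject at or above 1:8 before primary vaccination who is still there ten years later counts in the Month 120 results exactly as does one who seroconverted and kept the antibody. The plan does condition on the subject's own starting titre for its primary endpoint, where booster response is defined separately below and at or above 1:8, but not in the readable persistence comparison.

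Two things are at stake. The first is the quality of the comparison. Randomisation took place in study 036, in India, the Philippines and Taiwan. The subjects compared here come from one Philippine site, returned after ten years, and passed the filters of SAP 4.5. Balance on Month 0 titre in that subset is not assured, and one group is small. The second is reading. A single-group Month 120 percentage measures antibody present at that time, whereas the objective speaks of antibody that the vaccine induced.

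**Working it through.** **Inputs**
- Group sizes: 135 (ACWY-TT) and 45 (MenPS), from Protocol 10.3. They are planned for the Booster ATP cohort for immunogenicity; no size is planned for the persistence cohort. They reproduce from the text: 150 × 0.90 = 135, 50 × 0.90 = 45, total 180.
- Correlation ρ between Month 0 and Month 120 log titre: not given; assumed 0.2 to 0.5.
- Share at or above 1:8 at Month 0: not given; assumed 10% to 50%.

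**1. Is the unadjusted ratio biased?** Under randomisation, no. In 4,000 simulated trials of 135 and 45 with a true log2 difference of 1.0 (Month 0 SD 2.5, slope 0.4, residual SD 2.5), ANOVA averaged 1.008 (SD 0.468) and ANCOVA 1.007 (SD 0.437). The implied correlation is 0.4 × 2.5 / √((0.4 × 2.5)² + 2.5²) = 1/2.69 = 0.37.

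**2. What precision is given up?** The adjusted interval on the log scale is about √(1 − ρ²) times the unadjusted width.

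| ρ (assumed) | √(1 − ρ²) | Narrower by |
|---|---|---|
| 0.2 | 0.980 | 2.0% |
| 0.3 | 0.954 | 4.6% |
| 0.5 | 0.866 | 13.4% |

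The simulation agrees: 0.437/0.468 = 0.934, against √(1 − 0.37²) = 0.929.

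**3. How large could chance imbalance be?** The difference in mean Month 0 log titre has SD √(1/135 + 1/45) = 0.172 of a subject-level SD. The 95% range for the difference in the share at or above 1:8 is ±1.96 × √(q(1 − q)(1/135 + 1/45)), where q is that share:
- q = 10%: ±10.1 points
- q = 30%: ±15.5 points
- q = 50%: ±16.9 points

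A Month 0 imbalance of 1.96 of its own standard errors moves the unadjusted log GMT difference by about ρ × 1.96 of that difference's standard error: 0.59 at ρ = 0.3 and 0.98 at ρ = 0.5. Attrition that differs by group would come on top, and the documents give nothing from which to size it.

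**4. What do the percentages contain?** Let q now be the share at or above 1:8 at Month 0 who would be so at Month 120 whichever vaccine they had, and p the rate among the rest. The observed rate is q + (1 − q)p, so the group difference is multiplied by (1 − q). With assumed p of 90% and 60% (30 points apart):
- q = 10%: 91% and 64%, 27 points
- q = 30%: 93% and 72%, 21 points
- q = 50%: 95% and 80%, 15 points

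This happens under perfect balance, and a Month 0 covariate in the GMT model does not undo it. Only a display by Month 0 serostatus shows it.

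**The case against.** The strongest answer is that comparison with a randomised control is the ordinary way to isolate a vaccine effect. The objective is comparative, names its own measures, and Table 7 estimates those measures. Chance imbalance is sampling variation that the unadjusted interval already covers. The analyses are descriptive (Protocol 10.7), so no error rate is affected. Month 0 levels will appear beside Month 120 levels in the same cohort. All of this stands, and it limits the point to precision, protection against imbalance, and wording. It does not answer selection over ten years, which randomisation does not control, nor does it give a reason to leave unused a baseline value that the trial holds.

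A reader might infer three stronger things that the documents do not support.
- **That the plan disregards Month 0 altogether.** It is tabulated by group, and blacked-out parts may use it.
- **That a stated share of the Month 120 percentage is not vaccine-induced.** If 20% to 60% were seropositive at Month 0 and 90% stayed so, the product is 18 to 54 points. Both inputs are assumptions, and subjects seropositive at Month 0 were vaccinated too and may have been boosted.
- **That the Year 5 figures show background antibody.** Protocol 1.2 reports a range "between 34.9% - 93.0% in the subjects vaccinated with" the polysaccharide vaccine. That spread across serogroups would equally fit differences in vaccine response, waning or later natural exposure.

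The serostatus table will also be thin: 20% of 45 is 9 subjects, and even 9 of 9 gives an exact 95% interval of about 66% to 100%.

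**Conclusion.** The point holds in a limited form. In the readable text, the Month 120 GMT ratio is modelled on vaccine group alone and the differences in proportions are unstratified, while Month 0 titres are available for the same cohort. The ratio does not favour either vaccine in expectation. The loss is about 5% to 13% in interval width on the log scale at an assumed correlation of 0.3 to 0.5, and about 2% if the correlation is only 0.2. There is also no adjustment for Month 0 imbalance among ten-year returnees at one site with about 45 MenPS subjects. Single-group percentages should not be read as antibody induced by the vaccine. The size rests on assumed correlations and on group sizes planned for a different cohort.

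**What to change.** In SAP Table 7:
- Add an ANCOVA for the Month 120 GMT ratio with vaccine group and log10 Month 0 titre of the same serogroup. Handle Month 0 titres below the cut-off by the half-cut-off rule already in SAP 5.5.1. Report the adjusted ratio beside the unadjusted one, with the number of subjects in each model by group.
- Add a descriptive table of the percentages at or above 1:8 and 1:128 at Month 120 by Month 0 serostatus (below 1:8, at or above 1:8) within each group, noting that the MenPS strata will be small.
- Describe single-group results as antibody present at Month 120.

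The cost is SAP wording, one model and one table; no new data or sample size is needed. Subjects without a Month 0 titre drop out of the adjusted model, which is a reason to keep the unadjusted ratio in view. Adjustment cannot remove antibody from natural exposure during the ten years, so the wording change is needed whichever model is used. If a blacked-out part already does this, a cross-reference is enough.

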5.2. Subject identification and randomisation of treatment

5.2.1. Subject identification

Approximately 200 subjects are expected to participate in this study (150 from the ACWY-TT group and 50 from the MenPS group). Subjects will retain the same subject number as in MenACWY-TT-036 (109069).

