10.3. Determination of sample size

The sample size of this study with respect to the analysis of safety and immunogenicity post-booster is driven by the sample size of the primary vaccination study MenACWY-TT-036 (109069), the enrolment rate in the persistence extension study of MenACWY-TT-036 [MenACWY-TT-043EXT036 Y2, 3, 4 and 5 (112148)] and the estimated number of potential participating subjects based on the feedback from the site participating in this extension study. Subjects from the Philippines who received either MenACWY-TT or *Mencevax ACWY* vaccine will be eligible for this study if they meet the inclusion/exclusion criteria.

Subjects from the Philippines that were vaccinated in the MenACWY-TT-036 at the participating site will be invited to participate to this study with approximately 200 subjects expected to participate.

For the analysis at Month 121, one month after the booster vaccination, it is estimated that approximately 10% of the subjects will not be evaluable. Around 180 subjects will be included in the Booster ATP cohort of immunogenicity (135 in the ACWY-TT group and 45 in the MenPS group).

The primary objective of this study is to evaluate the immunogenicity of the booster dose in terms of the percentage of subjects with rSBA-MenA, rSBA-MenC, rSBA-MenW-135

and rSBA-MenY booster response.

Table 17 illustrates the precision one can expect for percentage of subjects with rSBA-MenA, rSBA-MenC, rSBA-MenW-135 and rSBA-MenY booster response from a group of 180 subjects.

Table 17 Exact 95% confidence intervals of the percentage of subjects with rSBA-MenA, rSBA-MenC, rSBA-MenW-135 and rSBA-MenY booster response

Approx. %	ACWY-TT group Exact 2-sided 95% CI (N =135)		MenPS group Exact 2-sided 95% CI (N =45)	
	Lower Limit (LL)	Upper Limit (LL)	Lower Limit (UL)	Upper Limit (UL)
20	13.6	27.7	9.6	34.6
30	22.8	38.9	18.2	46.6
40	31.7	48.8	25.7	55.7
50	41.6	59.1	35.8	66.3
60	51.2	68.3	44.3	74.3
70	61.9	77.9	55.7	83.6
80	72.3	86.4	65.4	90.4
90	84.1	94.8	78.8	97.5
100	97.3	100.0	92.1	100.0

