10.5. Derived and transformed data

10.5.1. Immunogenicity

- For a given subject and a given immunogenicity measurement, missing or non-evaluatable measurements will not be replaced. Therefore, an analysis will exclude subjects with missing or non-evaluatable measurements.
- The cut-off value is defined by the laboratory before the analysis and is described in [Section 5.7.3](#).
- A seronegative subject is a subject whose titre is below the cut-off value.
- A seropositive subject is a subject whose titre is greater than or equal to the cut-off value.
- The GMTs/GMCs calculations are performed by taking the anti-log of the mean of the log titre/concentration transformations. Antibody titres/concentrations below the cut-off value of the assay will be given an arbitrary value of half the cut-off value for the purpose of GMT/GMC calculation.
- rSBA booster response for serogroups A, C, W-135 and Y after the vaccine dose is defined as:
 - For initially seronegative subjects (pre-vaccination titer below the cut-off of 1:8): rSBA antibody titers post-vaccination titer \geq 1:32 one month after vaccination, and
 - For initially seropositive subjects (pre-vaccination titer \geq 1:8): rSBA antibody titers at least four times the pre-vaccination antibody titers, one month after vaccination.
- Handling of missing data: for a given subject and a given immunogenicity measurement, missing or non-evaluatable measurements will not be replaced.

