10.7. Interpretation of analyses

All the analyses will be descriptive with the aim to characterise the immunogenicity within CCI [REDACTED] study groups. CCI [REDACTED]
[REDACTED]

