**2. INTRODUCTION**

[figure not shown]
Subjects aged 11-17 years were vaccinated with 1 dose of either meningococcal group ACWY tetanus toxoid conjugate (MenACWY-TT) or Mencevax® ACWY in Study MenACWY-TT-036. The participants were further followed for the assessment of persistence in Study MenACWY-TT-043, and unless they withdrew their consent, they were invited for a yearly blood sample, regardless of their serostatus at the previous persistence time point, from Year 2 to Year 5 after primary vaccination. Five years after vaccination, the percentage of subjects with serum bactericidal assay using rabbit complement (rSBA) titers  $\geq 1:8$  ranged between 86.0%-97.5% in the subjects vaccinated with Nimenrix® and between 34.9%-93.0% in the subjects vaccinated with Mencevax ACWY.

The purpose of this study is to evaluate the safety and immunogenicity of a booster dose of MenACWY-TT vaccine administered 10 years after healthy subjects aged 11-17 years received either a single dose of meningococcal group ACWY tetanus toxoid conjugate (MenACWY-TT) vaccine or Mencevax ACWY. Study MenACWY-TT-036 was conducted in India, the Philippines and Taiwan. The MenACWY-TT-043 persistence study up to Year 5 after primary vaccination included only India and the Philippines. Due to Good Clinical Practice (GCP) issues in India, this booster study will only be conducted in the Philippines.

This SAP provides the detailed methodology for summaries and statistical analyses of the booster data collected in Study C0921005. Statistical analyses of persistence up to Month 120 are also described. This document may modify the plans outlined in the protocol; however, any major modifications of the primary endpoint definition or its analysis will also be reflected in a protocol amendment.

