## **5.5. Methods to Manage Missing Data**

### **5.5.1. Immunogenicity**

Missing immunogenicity data will be retained as missing. Meningococcal antibody titers and tetanus toxoid antibody concentrations below the cutoff will be set to 0.5\*cutoff before performing GMT/GMC calculations. The cutoff for each of the 4 meningococcal rSBAs is 1:8. The cutoff for the tetanus assay is 0.1 IU/mL.

Titers from blood samples exposed to temperature excursions may be excluded from the analysis. Determinations of exclusions will be on a case-by-case basis.

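### The Month 120 GMT ratio rests on a group-only ANOVA at a 3:1 split, so its 95% interval is not assured if the two groups' log-titre SDs differ

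*SAP*

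**What the plan says.** SAP Table 7 gives ANOVA as the method for the ratio of GMTs at Month 120, for each meningococcal group, in the ATP cohort for persistence. The footnote reads "Vaccine group as fixed effect in ANOVA model". No covariate, variance structure or sensitivity model is visible for this row.

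Protocol 5.2.1 expects "150 from the ACWY-TT group and 50 from the MenPS group". Protocol 10.3 expects "135 in the ACWY-TT group and 45 in the MenPS group" in the post-booster ATP cohort. No size is given for the Month 120 persistence cohort.

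Under Protocol 10.5.1, values below the assay cut-off "will be given an arbitrary value of half the cut-off value for the purpose of GMT/GMC calculation"; SAP 5.5.1 has the same rule. For the rSBA cut-off of 1:8 the assigned value is therefore 4.

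SAP Section 2 reports the Year 5 shares of subjects at or above 1:8. They are 86.0% to 97.5% for the conjugate vaccine and "between 34.9%-93.0% in the subjects vaccinated with Mencevax ACWY". The pairing by serogroup is not given.

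SAP 6.1.5 summarises titres "for each time point from Month 0, Month 1, and Month 120" in the same persistence cohort. Protocol 10.7 states: "All the analyses will be descriptive".

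**The concern.** A two-group ANOVA estimates one residual variance, weighted towards the larger group. The uncertainty of the ratio comes mostly from the smaller group. With three ACWY-TT subjects per MenPS subject, the pooled interval is too narrow if MenPS has the larger SD and too wide if it has the smaller one.

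Unequal SDs are plausible here. Every titre below 1:8 becomes the single value 4. In at least one serogroup at Year 5, about 65% of MenPS subjects were below 1:8 (100 − 34.9 = 65.1), against at most 14% of ACWY-TT subjects in any serogroup (100 − 86.0). Clustering at the floor can raise or lower a group's SD, depending on how far its other titres lie above the floor.

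Persistence relative to the polysaccharide vaccine is a stated secondary objective, and this ratio is one of its visible between-group estimates. If the interval method is chosen after the SDs are seen, the choice is post hoc.

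The row also leaves out the Month 0 titre. That costs some precision but does not make the interval invalid.

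**Working it through.** **Plan's own figures.** 150 × 0.90 = 135, 50 × 0.90 = 45 and 200 × 0.90 = 180, as in Protocol 10.3. All 18 exact intervals in Protocol Table 17 are reproduced to 0.1 (for example 27/135 gives 13.6 to 27.7, and 9/45 gives 9.6 to 34.6). The plan gives no precision figure for the GMT ratio.

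**Inputs.** n1 = 135 (ACWY-TT) and n2 = 45 (MenPS). r is the SD of log titre in MenPS divided by that in ACWY-TT, with the ACWY-TT SD set to 1. r is an assumption, varied from 0.5 to 1.5. The 95% level is taken from SAP 5.2, which states it for GMTs and GMCs; the ratio row shows no level.

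**Formulas.**

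- Pooled variance of the difference: [((n1 − 1) + (n2 − 1)r²)/(n1 + n2 − 2)] × (1/n1 + 1/n2)
- True variance of the difference: 1/n1 + r²/n2
- Approximate coverage: 2Φ(t × SE ratio) − 1, where t = 1.973 on 178 df and the SE ratio is pooled SE over true SE

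**Example, r = 1.5.** Pooled: (134 + 44 × 2.25)/178 = 1.309, and 1.309 × 0.02963 = 0.03878. True: 0.00741 + 2.25 × 0.02222 = 0.05741. SE ratio: √(0.03878/0.05741) = 0.822. Coverage: 2Φ(1.973 × 0.822) − 1 = 0.895.

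**Coverage at 135:45** (normal log titres, 40,000 simulated trials per row):

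| r | Pooled SE / true SE | Pooled coverage | Welch coverage |
|---|---|---|---|
| 0.5 | 1.365 | 99.2% | 95.0% |
| 0.7 | 1.190 | 98.1% | 95.1% |
| 1.0 | 1.000 | 94.9% | 94.9% |
| 1.25 | 0.895 | 92.0% | 95.0% |
| 1.5 | 0.822 | 89.4% | 95.1% |

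A second simulation with 100,000 trials per ratio gave 99.2%, 95.0%, 92.2% and 89.4% at r = 0.5, 1.0, 1.25 and 1.5. Pooled results at 150:50 agree within 0.3 points. At 90:90 the pooled and true variances are both (1 + r²)/90, so the SE ratio is 1.000 for every r. The sensitivity therefore comes from the 3:1 split.

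**What the floor can do.** Two illustrations at 135:45, both resting on assumed titre distributions rounded down to two-fold steps:

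1. A share of subjects sits at titre 4. ACWY-TT seropositives have mean log2 titre 7 to 9 and SD 1.5. Year 5 shares are paired lowest with lowest (86.0/34.9) and highest with highest (97.5/93.0).
   - Same titres in MenPS seropositives: r = 1.11 to 1.22, pooled coverage 92 to 94%.
   - MenPS seropositives two doublings lower: r = 0.70 to 1.02, pooled coverage 95 to 98%.
   - Welch: 94.3 to 95.3%.
2. One underlying normal distribution per group, floored at 4.
   - MenPS share 34.9%, equal underlying SDs (2 or 2.5 log2): r = 0.53 to 0.59, pooled coverage about 99%.
   - MenPS share 93.0%, equal underlying SDs: pooled coverage 94 to 96%.
   - MenPS share 93.0%, larger assumed MenPS SD (r about 1.3 to 2.05): pooled coverage 84 to 92%.
   - Welch, all cases run: 94.1 to 95.3%.

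**The replacement model.** Group plus Month 0 titre, group-specific variances and Satterthwaite df gave 94.7 to 95.5% coverage for r from 0.5 to 1.5. Its interval was about 2% narrower than Welch at an assumed Month 0 correlation of 0.2, and 7 to 8% narrower at 0.4. With floored titres it held 94.8 to 95.2% and was 3 to 4% narrower at an assumed correlation of 0.3.

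**The case against.** The strongest reply is that no error has been shown. The documents give no SDs, no Month 120 shares and no persistence-cohort size. If the floor dominates in MenPS, the planned interval is conservative. Coverage below 92% needs assumptions beyond the first floor illustration. This stands, and it is why the point concerns an unprotected assumption and not a known bias. Over-coverage is still a cost: at r = 0.5 the mean half-widths are 0.306 pooled and 0.225 Welch (in ACWY-TT SD units), so the planned interval would be about a third wider than needed.

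Second, between-group methods are redacted in both documents, and the footnote does not name a variance structure. Pooled variance is the ordinary reading of ANOVA, not a statement in the SAP. This also stands: if the redacted text sets group-specific variances, the coverage point falls away.

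Third, the effect is modest and partly visible elsewhere. At r = 1.22 and an assumed ACWY-TT SD of 1.5 log2, the interval is the ratio multiplied or divided by about 1.45 (pooled) or 1.52 (Welch). Each group's GMT has its own t-based interval, from which a reader could rebuild the Welch result. No margin or test for this ratio is visible. These facts limit the consequence, but the prespecified ratio interval would still be the one reported.

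Fourth, the Month 0 covariate is optional. Its gain depends on a correlation the documents do not give, and subjects without a Month 0 titre drop out of the adjusted model. Both are true, so the unadjusted Welch ratio belongs beside it.

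**Conclusion.** The concern holds for the visible method. A pooled-variance, group-only ANOVA at 3:1 does not assure 95% coverage for the Month 120 GMT ratio. Over SD ratios of 0.5 to 1.5, coverage runs from 99.2% down to 89.4%, and an unequal-variance interval stays at about 95%. Which part of that range applies cannot be known from the documents.

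The conclusion assumes that ANOVA means one pooled variance, that the ratio interval is meant to be 95%, and that the persistence cohort keeps roughly the 3:1 split. The variance part of the remedy protects coverage; the Month 0 part adds precision only.

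The change is worth making, but its reach is limited. The comparison is secondary and descriptive, the proportion differences in the same table do not need equal variances, and the primary booster-response analysis is unaffected.

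**What to change.** Replace the Table 7 footnote with: linear model on log titre with vaccine group and log Month 0 titre, group-specific residual variances and Satterthwaite degrees of freedom, back-transformed to a GMT ratio with a two-sided 95% CI. Report the unadjusted Welch ratio and its 95% CI alongside. Keep subjects without a Month 0 titre in the Welch ratio and state their number. If redacted text already sets the variance structure, align the footnote with it. Settle this before the Month 120 SDs are seen.

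The cost is one footnote and a few lines of code, with no new data. When the SDs are equal, the Welch interval is about 0.8% wider than the pooled one. The adjusted ratio will not equal the quotient of the two raw GMTs, which the table should note.
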